for Cho we have demonstrated that self-report can significantly underestimate actual intake (60). Thus, we need a set of biomarkers with which to assess Cho status in people. The largest stores of Cho are located in the liver, and mass resonance spectroscopy of liver has been used in the past to assess Cho status in humans (3, 25, 51). This method is not practical for use as a biomarker in clinical or public health practice as it is expensive and the availability of the instrumentation is limited. Liver biopsy is risky and not practical, making measurement of hepatic Cho and Cho metabolite concentrations a poor choice for assessing Cho status. Measurement of Cho concentrations in plasma alone is not an adequate marker for Cho status because Cho concentrations drop quickly to 70% of normal when a person is fed a low Cho diet, but do not decrease further with more severe depletion (3, 4) even in people starved for 7 days (61). The concentrations of PtdCho and sphingomyelin also decrease in people fed a low Cho diet (3, 4), but these phospholipids alone are not adequate biomarkers for Cho status because they are carried as part of plasma lipoproteins, and vary in concentration with changes in fat and cholesterol transport by these particles. Thus, such measurements are useful but not sufficient as biomarkers for Cho status.

Perhaps there is a panel of biomarkers that together will more accurately and reliably reflect Cho status. We admitted people (n=169; 60 premenopausal women, 52 postmenopausal women and 57 men) to our CTSA and fed them a diet containing 100% of recommended intake (550 mg/d) for one week, and then fed them a low Cho diet (10% normal Cho) for up to 7 weeks, or until they developed liver or muscle damage, and then fed them a Cho replete diet until such damage was completely resolved (24, 25, 52, 55). In these carefully controlled studies, using n=44 of the subjects, a comparison of metabolomic profiles between the two diet periods identified a number of potentially useful biomarkers of Cho status (10) (**Figs 2 & 3**).

The concentrations of plasma Cho, betaine, sarcosine, dimethylglycine, methionine, and PtdCho were significantly decreased, and homocysteine was significantly increased during Cho depletion in people (10). Cho

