On the last 5 days of a diet period, subjects will consume 22% of their total dietary Cho in the form of Cho chloride-(trimethyl-d9; 98%; Cambridge Isotope Laboratories, Tewksbury, MA, USA). This proportion was shown by others to result in adequate enrichment of isotopic Cho in adults (89). This Cho will be diluted in the plasma pool of Cho and then in the liver and total body tissue pool of Cho, and metabolites will be formed (**Figure 5, appendix**). We will collect a plasma sample before (baseline) and after (post dosing) each 5-day feeding of deuterated Cho.

Cho is stored in the body primarily as Cho, phosphoCho, glycerophosphoCho, PtdCho and sphingomyelin. Acetylcholine and CDP-Cho constitute a very small portion of the Cho pool and will not be measured. In plasma, phosphoCho is hydrolyzed to Cho by alkaline phosphatase; thus, measuring enrichment of Cho includes a measure of phosphoCho. New Cho enters the pool from the diet and from *de novo* synthesis catalyzed by PEMT. The sum of the metabolite enrichments of Cho-d9, glycerophosphoCho-d9, sphingomyelin-d9 and PtdCho-d9 will be calculated relative to the sum of Cho compounds with no d9. The presence of Cho d3 compounds will be a measure of recycling of a methyl group into Cho via the PEMT pathway, and will be considered to be part of the unenriched Cho pool. Betaine d3 will not be considered part of the Cho pool, but its formation will allow us to adjust our assumptions as to how much of administered label is lost from the Cho pool compartment. We expect that betaine formation will be significant.

Isotope enrichments in each of the Cho-containing compounds will be measured using LC-MS/MSAs described above (89). We will calculate enrichment for each Cho-containing molecule as well as for the combination of the Cho molecules (total); we expect that total Cho enrichment will be what is used in our analyses, but examination of the enrichment of the individual Cho-containing species may allow us to refine our mathematical

compartment models for Cho distribution at 5 days.

Estimated total body Cho pool size is calculated using the following mass balance equations:

$$1. \quad (F_a \times a) + (F_b \times b) = (F_c \times c)$$

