Where F_a is the isotope abundance of deuterium in the isotopic dose; a is the amount of the absorbed isotopic dose (absorption assumed to be 100%); F_b is the isotope abundance of deuterium in the endogenous Cho pool (measured at baseline before 5-day deuterium treatment); b is the amount of the endogenous Cho pool at baseline; F_c is the isotope abundance of deuterium in the total Cho pool ($F = {}^2\text{H}/[{}^1\text{H} + {}^2\text{H}]$) after 5-day dosing; c is the amount of the total Cho pool after dosing.

F_a , F_b and F_c are measured by isotope ratio mass spectrometry.

a is calculated from administered dose

$$2. \quad c = a + b$$

$$3. \quad b = \text{body pool at baseline (unknown)} = a \frac{(F_a - F_c)}{F_c - F_b}$$

Though we will call the estimate derived from the above a measure of total body pool size, it is really just an estimate of the size of the pool that dietary Cho equilibrates with by 5 days (likely smaller than the total body pool). We must make a number of assumptions, discussed below, to arrive at such an estimate. Each assumption certainly affects our estimations of pool size, and as we collect data we will have to model outcomes if we alter these assumptions.

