The use of isotope dilution to estimate Cho pools size has not been used before, but as noted above is an approach that has been proved successful for total body water (90) and Vitamin A (12). For both of these methods, a single bolus of isotopic label can be used. For both of these it is important that the isotopic label equilibrates rapidly with the body pool. We know that Cho equilibrates within minutes with the vascular and liver pools of Cho, but that equilibration with the PtdCho-bound Cho takes hours to days. For this reason, we propose to administer deuterated Cho for 5 days. We realize that our diet depletion protocol will result in a decline in body pool size during these 5 days, but suggest that the decline during the previous 11 days will be larger and make the resulting error in pool size estimation acceptable. Caudill used 3 weeks as her equilibration period (89), but such a long period would provide an estimate of average Cho pool size during the diet intervention rather than at the end of the intervention. Based on our best estimates of Cho turnover in the free and esterified pools, we believe that a 5-day isotope equilibration will work best for the purposes of the study. The equation for calculating Vitamin A total body pool also includes a correction factor for efficiency of absorption of Vitamin A (12). For Cho, we are assuming that efficiency of absorption is 100% (studies described below in SubAlm 1a will help us to test/revise this assumption). This likely is an overestimate, but will result in an overestimation of pool size that will be a constant error for all diet periods, thereby the calculation of the change in pool size caused by a diet period should not be appreciably altered. Similarly, the assumption that little Cho is lost to renal excretion is not true, as the metabolites betaine and TMA are excreted in the urine. Such losses of label in urine will result in an underestimate of Cho pool sizes, but this underestimation of pool size will be a constant error for all diet periods, and changes in pool size should not be affected. We also assume

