that *de novo* formation of PtdCho by phosphatidylethanolamine N-methyltransferase (PEMT) during the 5 days of isotope administration is small compared to body pool size; in women with estrogen this dilution of isotopic label would be greater than in men and postmenopausal women. We believe that the contribution of PEMT will not appreciably change the estimates of pool size that we obtain. To reiterate, as long as the assumptions are uniform in the equation used across diet periods, treatment effects should not be affected.

We propose to use deuterium labeling rather than ^{13}C . The natural abundance of deuterium is $\sim 0.015\%$ compared to hydrogen at $>99.9\%$, whereas those of ^{13}C and ^{12}C are 1.1% and 98.9% , respectively. This makes it easier to attain satisfactory enrichment with lower doses of deuterium. However, deuterium can shift within or between molecules through proton exchange, but this usually occurs under harsh conditions (12). The Caudill data using deuterated Cho suggests that proton exchange is not a significant problem in human studies (89). Using d9-Cho relative to 1,1,2,2-d4-Cho allows us to better differentiate by mass (9 vs 4 mass units). Deuterium labeled Cho is also 6x less expensive than ^{13}C -Cho.

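### The isotope-dilution equation omits unlabelled choline eaten between dose and sample, so the error in baseline pool size b differs by diet and is not constant

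*Combined protocol and SAP*

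**What the plan says.** The primary objective (section 2.1) is to correlate a biomarker score with choline pool size measured by isotope dilution. Section 6.3 uses that pool size as the response when biomarker weights are set.

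Section 5.1 gives three equations. Equation 1 balances label: Fa·a + Fb·b = Fc·c. Equation 2 sets the total after dosing to c = a + b. Equation 3 solves for b = a(Fa − Fc)/(Fc − Fb). The target is explicit: "b is the amount of the endogenous Cho pool at baseline". In rejecting a three-week labelling period, the same section says that this "would provide an estimate of average Cho pool size during the diet intervention rather than at the end of the intervention", so the end-of-period pool is also of interest.

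On sources of choline the section states "New Cho enters the pool from the diet and from" de novo synthesis. On errors it considers incomplete absorption, urinary loss, pool decline during labelling and de novo synthesis. Of urinary loss it says "Such losses of label in urine will result in an underestimate of Cho pool sizes" and that "this underestimation of pool size will be a constant error for all diet periods, and changes in pool size should not be affected". It then generalises: "as long as the assumptions are uniform in the equation used across diet periods, treatment effects should not be affected".

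The equations are worded for five days of labelled food. The synopsis and sections 3.1, 4.2 and 7 instead give a single 250 mg bolus on Day 12. In section 4.2, subjects collect meals for Days 12-14 at the bolus visit and give a last blood sample on the morning of Day 15. No separate equation is given for the bolus, and no text names the Fc sample for it.

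**The concern.** Unlabelled choline eaten after the dose dilutes the label just as baseline choline does. Equation 2 has nowhere to put it, so equation 3 attributes it to b. The amount is daily intake times elapsed days, and daily intake is the randomised factor. Using one equation for all diets does not give one error for all diets when the omitted term is the diet itself. Dietary dilution is not among the error sources that section 5.1 discusses.

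Pool size is the reference for the whole panel. A reference error that rises with current intake favours markers of recent intake over markers of status when weights and importance scores are set.

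**Working it through.** **Inputs from the documents.** Intake I = 550, 275 and 137.5 mg/d (synopsis). Dose a = 250 mg, with label purity giving Fa = 0.98. Time from dose to sample t = 3 days, taking Fc from the Day 15 sample because the synopsis places the isotope measurement at the end of the period.

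**Assumed.** True pool b = 5-40 g, because the documents give none; outflow O; one well-mixed pool.

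**Check of the printed algebra.** With b = 10 g and no intake after the dose, equation 3 returns 10 g, so it follows from equations 1 and 2. The plan states no figure for pool size or its error, so there is nothing else to reproduce.

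**Error in b, no outflow, Fb = 0.** Fc = Fa·a/(a + b + I·t), so equation 3 returns b + I·t.
- 100% diet: 3 × 550 = 1,650 mg too high.
- 50% diet: 3 × 275 = 825 mg.
- 25% diet: 3 × 137.5 = 412.5 mg.
- 100% minus 25%: 1,237.5 mg.

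**Error in b, outflow equal to intake, Fb = 0.** Equation 3 returns (a + b)·exp[I·t/(a + b)] − a. At b = 10 g:
- 100% diet: 10,250 × exp(1,650/10,250) − 250 = 11,790 mg, an error of 1,790 mg.
- 25% diet: 10,250 × exp(412.5/10,250) − 250 = 10,421 mg, an error of 421 mg.
- Difference: 1,369 mg. At 5, 20 and 40 g it is 1,510, 1,302 and 1,270 mg.

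With outflow of 550 mg/d on both diets the difference is 1,263-1,447 mg. Outflow hardly matters for b.

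**Residual label from an earlier bolus.** Each subject takes a bolus in every period, with a minimum two-week washout. With outflow equal to intake, the share of enrichment left at the next bolus is about exp[−(3·I1 + 14·W + 11·I2)/b], where I1 and I2 are the two diets and W is washout intake (assumed 300-550 mg/d). The exponent's numerator runs from 412.5 + 4,200 + 1,512.5 = 6,125 mg to 1,650 + 7,700 + 6,050 = 15,400 mg. The share is therefore 5-29% at 5 g, 21-54% at 10 g and 68-86% at 40 g, so Fb cannot be taken as zero after the first period.

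Example with b = 10 g, no outflow, and Fb at half the initial bolus enrichment: 0.5 × 0.98 × 250/10,250 = 0.01195. Equation 3 returns a[b(Fa − Fb) + Fa·I·t]/[a(Fa − Fb) − Fb·I·t]. That is 12,706 mg on the 100% diet and 10,634 mg on the 25% diet, so the errors differ by about 2,071 mg. Over 10-40 g and the outflow scenarios the gap is 1.9-2.3 g.

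**Error against the end-of-period pool (a + b from equation 3), Fb = 0, 100% minus 25%.**

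| Outflow | Gap, pools 5-40 g |
|---|---|
| None | 0 |
| 550 mg/d on every diet | 26-209 mg |
| Equal to intake | 1,270-1,510 mg |

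**Sensitivity of the error in b (Fb = 0).**
- Fc on Day 13: 412-441 mg. Fc on Day 14: 825-941 mg.
- Intake scaled per 70 kg, no outflow: 1,237.5 × 55/70 = 972 mg; 1,237.5 × 85/70 = 1,503 mg.
- Bolus replacing bread choline on the 100% diet (section 7), no outflow: 1,237.5 − 250 = 987.5 mg.
- Five-day feeding at 22% label: 0.78 × 5 × 412.5 = 1,609 mg with no outflow, and 592-695 mg with outflow equal to intake. Returning to that regimen does not remove the problem.

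**Sign of label loss, bolus.** If a fraction f is lost before mixing, Fc falls and equation 3 returns about b/(1 − f). For f = 0.1, 10,000/0.9 = 11,111 mg, an overestimate; section 5.1 says underestimate. Loss from the mixed pool alone does not bias b. Under five-day feeding the sign depends on outflow.

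**The case against.** The sentence about a constant error concerns urinary label loss, not dietary dilution. That is correct, and a constant fractional loss would not alter correlations. The general sentence about uniform assumptions is the one that fails.

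The plan also anticipates refinement. SubAim 1a estimates label loss, section 5.1 promises to model altered assumptions and to use betaine formation to adjust for lost label, and spectroscopy offers an outside comparison. These could expose a problem, but none adds the missing intake term.

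The equation is worded for five-day feeding, so applying it to the bolus is an inference. No other equation is given, and the five-day version has the same gap. A single instantly mixed pool is a simplification too: section 5.1 says esterified choline equilibrates over hours to days. The milligram figures are therefore approximate.

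A reader might infer that diet effects on the end-of-period pool are wrong by 1.2-1.5 g. The documents do not support that. If outflow stays at 550 mg/d on every diet and there is no prior label, the end-of-period gap is at most about 0.2 g and the plan's constancy claim nearly holds. Section 5.1 says "We expect that betaine formation will be significant", and the earlier study reports that "The concentrations of plasma Cho, betaine, sarcosine, dimethylglycine, methionine, and PtdCho were significantly decreased". This hints that outflow falls on a low diet, but those are concentrations on a 10% diet, not fluxes on a 25% diet.

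**Conclusion.** The defect holds for b as the plan defines it. Equation 3 adds roughly three days of unlabelled intake to the baseline pool, so the claim that uniform assumptions protect treatment effects is wrong as written. The 100%-versus-25% difference in error is about 1.2-1.5 g in a label-free first period, and about 1.9-2.3 g at 10-40 g if Fb is half the initial bolus enrichment. Both ranges rest on a Day 15 Fc sample, one mixed pool and assumed pool sizes.

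For the end-of-period pool the size is open: 0 to about 1.5 g with no prior label, depending on outflow. It is also tempting to conclude that the primary correlation will be inflated by a known amount. The direction is clear, since markers of recent intake are favoured, and small pools are affected more. The amount depends on pool size and outflow, which the documents do not give.

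Confidence is high on the missing term and its direction, and low on its size for the end-of-period pool and on the correlation effect. This should be fixed before pool sizes are calculated. As a secondary point, the stated sign of label loss is wrong for label lost before mixing under the bolus.

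**What to change.** 1. Define a as the 250 mg Day 12 bolus, Fb as the 0 h Day 12 sample of that same period (measured, never set to zero) and Fc as the Day 15 sample. Remove the five-day text from sections 1.2 and 5.1.
2. Replace equation 2 with c = a + b + D, where D is assayed unlabelled choline intake from dose to sample. Equation 3 becomes b = [a(Fa − Fc) − Fc·D]/(Fc − Fb). State that this targets the pre-dose Day 12 pool. D must enter the balance: subtracting it from the old b still leaves 0.7-1.1 g between diets at 10-40 g when Fb is half the initial bolus enrichment. In the one-pool model the new equation leaves 0-260 mg at 10-40 g for Fb up to 70% of initial bolus enrichment. At 5 g it leaves 0-272 mg with Fb = 0 and up to about 650 mg with Fb up to 70%.
3. As sensitivity analyses, report uncorrected equation 3 and an end-of-period estimate corrected for label in the Day 12-15 urines. State that the latter depends on urinary recovery and on Fb: with outflow equal to intake, 20% recovery leaves 1,016-1,208 mg, and at Fb of 50% it can miss by 0.6-1.1 g. Give the score-pool correlation overall and within person for each.
4. Delete the section 5.1 claims that changes and treatment effects are unaffected, and correct the sign statement for the bolus.

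The cost is rewritten text and a small added analysis, with no new visits or samples. D uses diet assays already planned and brings in some intake-measurement error. The urine sensitivity analysis needs label assayed in urines that section 4.2 already collects.

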6 STATISTICAL CONSIDERATION

6.1 Primary Endpoint

SubAim 1a: Test assumptions used in the choline isotope dilution method for estimating choline pool size. In the subjects studied: a) collect urine after administration of deuterated choline and develop an estimate of % loss of administered label from body pool; b) measure choline pool size by isotope dilution and compare results

to changes seen using mass resonance spectroscopy (MRS) of choline compound peaks in liver (the major storage pool for choline); c) assess fatty liver by mass resonance imaging (MRI) and compare results to those obtained using Fibroscan methodology. These experiments will help us to refine the assumptions that we make to model choline pool size, and will validate the use of Fibroscan data as a measure of fatty liver.

SubAim 1b: Determine whether there are additional biomarkers from untargeted metabolomic profiling that, when added to the panel developed in Aim 1, are better at predicting choline status in people (using choline pool size determined by isotope dilution as a proxy for choline status). In the experiment described in Aim 1 we will add consideration of data from untargeted metabolomic profiles at the end of each diet period. This data will be used to identify metabolites that, when added to the biomarker panel developed in Aim 1, improve the correlation with choline pool size assessed using isotope dilution.

6.2 Secondary Endpoint

SubAim 1c: Determine whether people with genetic polymorphisms known to increase risk for developing choline deficiency-induced organ dysfunction are also more likely to have a worse choline status score and a reduction in choline pool size assessed using isotope dilution. A number of SNPs in genes of choline and folate metabolism have been associated with increased risk for developing organ dysfunction on a low choline diet. We hypothesize that people with these SNPs have a lower choline pool size/worse choline status score for any given choline dietary intake than do people without these SNPs.

6.3 Statistical Methods

Statistical methods (Aim 1, SubAim 1a,1b). Unsupervised principal component analysis will first be used to examine the clustering of samples from the diet periods, and to ensure that the QC pool replicates center in the samples from which they were derived. This will enable the evaluation of the stability of the platform across the plate and between days for the signals which have not yet been assigned, to remove any signals that are too random and prevent the desired clustering, and to identify subjects who outlie from their perspective diet periods. Supervised Orthogonal Partial Least Squares Regression (OPLS-R) will then be used to identify a panel of biomarkers, assign weight to each biomarker, and calculate a composite score to predict choline pool size. When we applied Orthogonal Partial Least Squares Effect Projections (OPLS-EP) and Orthogonal Partial Least Squares Discriminant Analysis (OPLS-DA) to our previous data, we identified a panel of biomarkers and calculated a composite score that successfully predicted choline status (baseline or depletion) for both men and women (**Figure 1**). In this proposed study, we will use OPLS-R instead of OPLS-DA, because choline pool size is a continuous variable, while choline status in our previous study was a categorical variable. We will analyze all of the samples using OPLS-R to identify a panel of biomarkers that predicts choline pool size universally for all three diet periods (healthy men, pre- and postmenopausal women). We will also consider performing the analysis for each diet period separately in case the universal panel does not provide high accuracy in prediction. For the purpose of validation, we will not split samples into training and testing sets, as it reduces the number of samples used for model building. Instead, prediction error will be estimated using the Bootstrap method, which was found by recent studies as providing “nearly unbiased estimates of future model performance without holding back data when making the final estimates of model parameters” (101). Variable Importance to Projection (VIP)

score will be calculated based on the OPLS weights and the variability explained in OPLS-R. Biomarkers with $VIP > 1.5$ will be considered the most important biomarkers responsible for prediction. Pathway analysis will be performed using GeneGo metacore (Thomson Reuters, <https://portal.genego.com>) and QIAGEN's Ingenuity Pathway Analysis (IPA®, QIAGEN Redwood City, www.qiagen.com/ingenuity).

Statistical methods (SubAim 1c). Linear model with repeated measures will be used to identify SNPs that increase (or decrease) the risk for developing choline deficiency-induced organ dysfunction. This analysis will be performed for each diet period (healthy men, pre- and postmenopausal women) separately. In each linear model, the choline status score defined by Aim 1 is the response variable. Diet effect (fixed), genotype effect (fixed), subject effect (random) and diet \times genotype interaction effect are the independent variables. In the repeated measures design, each subject serves as his/her own control. Therefore, confounding effect from genotype is not our concern. However, it is possible that genotype serves as a moderator, which interacts with the diet effect, and affects the direction or strength of the diet effect. For example, the change in choline status score in responding to dietary choline may be observed in subjects with one genotype (responders), but not in subjects with other genotypes (non-responders). The genotypes that modify the diet effect will be identified by the diet \times genotype interaction term. This analysis will be performed in the MIXED procedure in SAS (SAS Institute, Inc., Cary, NC). Benjamini-Hochberg method for False Discovery Rate (FDR) correction will be used for multiple testing correction. To improve the normality of the data, data transformation such as log transformation will be applied to metabolomics data, and outliers with studentized residue > 3 or < -3 will be excluded. Post hoc comparisons will be performed to identify metabolites associated with different levels of dietary choline and different genotypes. The analysis described above will also be applied to choline pool size data to identify significant diet \times genotype interaction effect for choline pool size.

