2 STUDY OBJECTIVES

The goal of this study is to identify a biomarker panel that correlates well with measured Cho pool size across a range of different degrees of Cho depletion. We hypothesize that, as body stores of Cho diminish, cells and organs will reach the point when metabolism/function in the cell is altered, and that this will result in a progression of changes in biomarkers that reflect Cho status.

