2.1 Primary Objective

Determine whether, in people, a choline status score based on measurements of a panel of biomarkers correlates well with measures of choline pool size as assessed using an isotope dilution method.

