3.1 Study Design

This is a crossover study wherein each subject will serve as their own control. Comparisons will be made between the low choline diet periods to the 100% choline diet at the beginning and end of the 6 weeks on the three dietary intervals (see Fig. 1, Appendix).

Screening: Before entry to the study the participants will be seen at the University of North Carolina Nutrition Research Institute Outpatient Clinical facility where a physical exam by a physician and a Clinical Chemistry panel will be performed to ascertain that they are healthy. Subjects will have mass resonance spectroscopy to measure Cho compounds in liver, and mass resonance imaging to assess fatty liver to validate the isotope dilution methodology and Fibroscan technology, respectively.

Intervention: Recruited subjects will be asked to fill out the Automated Self-Administered 24-hour Dietary Assessment Tool (ASA24) found on the NCI web site (<https://epi.grants.cancer.gov/asa24/>) for 3 days the week prior to the first diet intervention. This will estimate the choline intake level for subjects beginning the study. The week after screening, subjects will be placed on one of the three dietary choline levels (100%, 50%, and 25% - order randomly assigned) with a minimum 2 week washout between. On day 12 of each diet period, subjects will receive a 250mg bolus dose of the Cho delivered as Cho-d9 in order to estimate Cho pool sizes by isotope dilution (see Fig. 1, Appendix).

Follow-up: If the clinical laboratory data remain within normal values, this will conclude the subject's participation. If not, see section 4.3 (below).

Unscheduled Visits: Subjects may have to make unscheduled visits to pick up food if their freezer storage space is limiting.

3.2 Allocation to Treatment Groups and Blinding (if applicable):

All subjects will be randomly assigned to the order of the diet interventions. Investigators making metabolite, MRI, MRS, or Cho pool analyses will be blinded to diet assignments.

3.3 Study Duration, Enrollment and Number of Subjects:

The study lasts 10 weeks and a few days for each subject. We plan to enroll 150 subjects: 50 males, 50 pre-menopausal females, and 50 post-menopausal females. We will recruit an additional 30 subjects to account for drop out replacement, so the total number of subjects is 180.

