6.4 Sample Size and Power

Sample size estimation (Aim 1, SubAim 1a,1b). Similar to OPLS-DA, OPLS-R is a multivariate method for prediction. Different from hypothesis testing methods such as t-test or ANOVA, where sample size is determined by the power of rejecting null hypotheses when the alternative hypothesis is true, the sample size of OPLS-R is determined by its accuracy of prediction. In this study, we propose to recruit three groups of subjects (healthy men, pre- and postmenopausal women) with $n=60$ /group (estimated that $n=50$ /group will complete study). We plan to analyze all three groups together ($n=50*3=150$ subjects) to identify a formula for composite score that can predict choline pool size for all three groups. In case the universal score does not perform well, we will analyze each group ($n=50$ subjects) separately. Using our previous data with $n=44$ subjects, we successfully identified a panel of metabolites that can be used to predict whether a sample is taken at baseline or after choline deficient diet. As shown by the ROC plot, the area under curve was 98.77%, which indicates very high sensitivity and specificity (Figure 2). Our previous study indicates that there is a strong association between the panel of biomarkers and choline status even when the model was developed with a relatively small number of samples.

Sample size estimation (SubAim 1c). This analysis will first be applied to the *PEMT* SNPs (rs12325817-C; rs4646343-A and rs3760188-A) that are known to interact with the effect of dietary choline in women but not in men (24). This analysis serves to confirm the consistency between the performance of the choline status score and existing knowledge. Assuming the effect size of the diet \times genotype interaction is 0.6 (moderate effect), we

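### Aim 1 judges the choline score by pooled prediction only; no stated analysis tests whether a person's change in score follows that person's change in pool size

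*Combined protocol and SAP*

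**What the plan says.** Section 2 sets the goal as a panel that "correlates well with measured Cho pool size across a range of different degrees of Cho depletion". The primary objective (2.1) is a score that "correlates well with measures of choline pool size as assessed using an isotope dilution method", without saying whether the correlation is between people, within people, or both. Section 3.1 gives the design: "This is a crossover study wherein each subject will serve as their own control".

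The Aim 1 analysis (synopsis, Statistical and Analytic Plan; section 6.3) is one OPLS-R: "We will analyze all of the samples using OPLS-R to identify a panel of biomarkers that predicts choline pool size universally". No subject term, person-centring or change score is mentioned. Prediction error is to come from a bootstrap, and the unit resampled (person or sample) is not stated. Section 6.3 says that the earlier data were analysed with both an effect-projection method (OPLS-EP) and OPLS-DA. It replaces OPLS-DA with OPLS-R and names no counterpart to the effect projection.

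The fallback appears in two forms. Section 6.3 has: "We will also consider performing the analysis for each diet period separately in case the universal panel does not provide high accuracy in prediction". Section 6.4 has: "In case the universal score does not perform well, we will analyze each group", with 50 subjects per group. The synopsis and 6.3 also describe the target as "universally for all three diet periods (healthy men, pre- and postmenopausal women", so the three groups of people stand as the explanation of the term diet period.

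**The concern.** The claim the trial wants to make is about depletion: as the pool shrinks, the score should move. Appendix Figure 4 is drawn in those terms. A pooled correlation mixes two things: whether people with larger pools have higher scores, and whether a person's score moves when that person's pool changes. Any stable characteristic related to both score and pool size feeds the first and says nothing about the second. If only the pooled figure is reported, a reader cannot tell which of the two has been shown.

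The plan's own defence of its reference measure makes this matter more. In 5.1 the isotope method is said to carry errors in absolute pool size from assumed complete absorption and neglected urinary loss. These are accepted because they should be constant across a person's diet periods and leave changes intact. The same section says that label dilution by the body's own choline synthesis is greater in women with estrogen than in men and postmenopausal women. That argument supports within-person change. It does not cover absolute levels compared across the three groups, which the pooled fit uses.

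**Working it through.** **The plan's own numbers.** Completers: 50 × 3 = 150. Recruited: 60 × 3 = 180, and 150 / (1 − 1/6) = 180. Both reproduce. Section 6.4 bases the Aim 1 size on prediction accuracy and gives no variance, precision target or power, so there is no Aim 1 calculation to repeat. Full data would give 150 × 3 = 450 end-of-period samples.

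**What SubAim 1c adds.** Its mixed model (6.3) has diet, genotype, their interaction and a random subject effect. The response is the score and, in a separate run, pool size. It can show that each variable shifts with diet on average. Score and pool size never appear in the same model, so it cannot show that one follows the other within a person.

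**How large a pooled correlation can be without tracking.** Let ICC be the between-person share of variance (taken equal for score and pool size), r_B the between-person correlation and r_W the within-person correlation. Then

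pooled r = ICC × r_B + (1 − ICC) × r_W.

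ICC, r_B and r_W are all assumptions. With r_W = 0:

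| ICC | r_B = 0.7 | r_B = 0.9 | r_B = 1.0 |
|---|---|---|---|
| 0.3 | 0.21 | 0.27 | 0.30 |
| 0.5 | 0.35 | 0.45 | 0.50 |
| 0.7 | 0.49 | 0.63 | 0.70 |
| 0.9 | 0.63 | 0.81 | 0.90 |

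A simulation of 150 people on 3 diets (600 runs per cell, diet assumed to carry 5% of pool-size variance) gave the same values. The within-person correlation and the correlation of changes between the two extreme diets were about 0 in every cell.

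For contrast, a score that does track (r_W = 0.8, r_B = 0.9, ICC = 0.5) gives 0.5 × 0.9 + 0.5 × 0.8 = 0.85. That lies between the 0.81 and 0.90 of the last row, where tracking is nil. The pooled value alone cannot separate the two cases.

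**The two fallbacks.** By group: 50 people × 3 diets = 150 samples, with all three diets kept for each person. By diet period, read literally: 150 people × 1 diet = 150 samples, with diet constant. In the simulation the by-diet correlation was slightly higher than the pooled one (0.65 against 0.63 at ICC 0.7, r_B 0.9), because the diet variance is removed. A literal by-diet refit could therefore look like an improvement while carrying no information on depletion.

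**Whether the planned size supports a within-person analysis.** Repeated-measures correlation, Fisher z, two-sided alpha 0.05 (assumed): df = n(3 − 1) − 1, and detectable r = tanh[(z for alpha + z for power) / √(df − 1)].

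- n = 150, df = 299: tanh[(1.96 + 0.84)/√298] = 0.16 at 80% power; 0.19 at 90%.
- n = 50, df = 99: tanh[(1.96 + 0.84)/√98] = 0.28 at 80% power; 0.32 at 90%.

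**The case against.** Four points on the other side deserve weight.

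- **Between-person prediction is wanted.** Section 1.1 (Impact) has clinicians identifying people with depleted stores, and a pooled fit answers that. This stands: a reader who concludes that the pooled score would be worthless goes too far.
- **Zero within-person response is an extreme case.** The panel in 5.1 draws largely on markers that changed within people in the earlier 10% diet study. In Appendix Figure 3 choline fell 29 to 34% and betaine 47 to 55%. Liver fat, which CAP measures, is itself treated as a depletion marker. This stands as a reason to expect some tracking. It does not replace testing for it, particularly as the synopsis expects smaller differences here.
- **SubAim 1c would expose a score that ignores diet.** True for the average shift, and it limits the risk. It leaves the person-level link untested.
- **The fallback wording is a slip.** A reader might infer from the literal text that the fallback discards the diet contrast altogether. The documents do not support that. The synopsis and 6.3 gloss diet periods as the three groups of people. Section 6.3 uses the same gloss for the SubAim 1c model, which contains a diet effect and so could not be run within one diet. Section 6.4 states the fallback by group.

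**Conclusion.** The gap is real and cheap to close. As written, Aim 1 can show that the score predicts pool size across all samples. It cannot show that the score follows a person's own depletion or repletion.

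The size is uncertain because no variances are given: pooled r of about 0.2 to 0.9 with no within-person association, over ICC 0.3 to 0.9 and r_B 0.7 to 1.0. The upper end needs both to be very high.

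One might infer that a trait-only score would almost certainly correlate near 1. With a 10% lower pool on the lowest diet and a between-person log-SD of 0.15 to 0.25, such a score would reach 0.96 to 0.99. But that assumes a perfect trait measure and no residual variance in pool size. Even on those terms the figure is 0.85 for a 20% fall with SD 0.15, and 0.74 for a 20% fall with SD 0.10. It is a ceiling under chosen inputs, and nothing in the documents fixes those inputs.

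The fallback is a wording inconsistency to be reconciled. It is not evidence that the diet contrast will be lost.

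**What to change.** In section 6.3, and in the matching synopsis text:

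1. Beside the pooled result, report the within-person correlation and the within-person slope of score on pool size, with confidence intervals. Either centre both variables on each person's mean over the diets, or fit a mixed model that separates the person mean of pool size from the deviation around it.
2. Compute these from bootstrap-validated scores, and resample persons rather than samples, so that a person's diet periods stay together.
3. State that the score will be said to track depletion only if the within-person association is positive (score oriented so that higher means a larger pool).
4. Change the fallback from each diet period to each sex/menopause group, to agree with its own gloss and with 6.4.

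An OPLS-R on person-centred data is an optional sensitivity analysis.

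The cost is SAP wording and one further analysis of data already planned, with no added participants or measurements. The downside is that the within-person figure will probably be less favourable than the pooled one.
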